## 8.5.2. Assessment of laboratory/procedures abnormalities

For every laboratory/procedure assessment, the investigator will evaluate if the laboratory/procedure test is normal or abnormal. If abnormal (after repeat testing), the investigator will assess if this finding is "clinically significant" or not.

An abnormal lab/procedure test must be compared with the previous value taking into account normal values in the studied population/country.

If a laboratory/procedure parameter is **abnormal AND** the abnormality assessed **clinically significant**, it should be reported as an AE.

An AE is a new event after the administration of at least one tablet of the study drug or a worsening in the condition (in the case of laboratory/procedure tests, it is an increase in severity (clinical intensity) of the abnormality) which is judged clinically significant by the investigator.

Laboratory/procedures (i.e. ECG...) abnormalities (or worsening in severity or frequency of pre-existing abnormalities) should be assessed as "clinically significant" (and therefore have to be reported as an AE) if they meet at least one of the following conditions:

• The abnormality suggests a disease and/or organ toxicity **AND** this abnormality was not present at the screening visit or is assessed as having evolved since the screening visit

• The abnormality requires medical intervention or concomitant therapy

When reporting an abnormal lab/procedure as an AE, a syndromic **clinical diagnosis should be recorded** (if available) rather than the abnormal value itself (e.g. acute pancreatitis instead of each finding separately: high levels of amylase, high levels of lipase, abdominal pain and vomiting; e.g. "hypokalaemia" rather than "decreased potassium levels"; "anaemia" rather than "decreased red blood cell count").

## 8.5.3. Serious adverse event

An AE will be defined as serious if :

- It is fatal: i.e. causes or contributes to the death.
- It is life-threatening: in this context refers to an AE in which the subject was at risk of death at the time of the AE; it does not refer to an AE that hypothetically might have caused death if more severe.
- It requires or prolongs hospitalisation: i.e. the AE requires at least an overnight admission or prolongs a hospitalisation beyond the expected length of stay. Hospital admissions for surgery planned before study entry, for social reasons, for any elective surgery (i.e. plastic surgery) or per protocol or for normal disease management (including treatment adjustment) are NOT to be considered as SAE according to this criterion.
- It results in persistent or significant disability: i.e. the AE resulted in a substantial disruption of the subject's ability to conduct normal activities.
- It is a congenital anomaly/birth defect: i.e. an AE outcome in a child or foetus of a subject exposed to the Investigational Medicinal Product before conception or during pregnancy.
- It is an important medical event: i.e. is medically significant. Medical and scientific judgment should be exercised in deciding whether other situations should be considered serious events/reactions, such as important medical events that might not be immediately life-threatening or result in death or hospitalisation but might jeopardise the subject or might require intervention to prevent one of the other outcomes listed above. Any suspected transmission via a medicinal product of an infectious agent is also considered a serious AE.

The Investigator will assess the seriousness of all AEs as serious or non-serious and record the assessment in the electronic case report form (eCRF) along with the following information:

- SAE onset/start date: Start date of SAE or date when the AE becomes serious (see seriousness criteria of an SAE).
- SAE end/stop date: SAE end date is the date of AE recovery.

## 8.5.4. Eliciting adverse event information

The investigator is required to report all directly observed AEs and all AEs spontaneously reported by the trial subject using concise medical terminology. In addition, to avoid bias in eliciting AEs, each trial subject will be questioned about the occurrence of AEs during hospitalisation period and study follow-up visits, with general, non-leading questions such as *"Since xxx (e.g. last visit) have you had any health problem?"* or *"How are you feeling?"* 

All AEs (serious and non-serious) must be recorded on the source documents and CRFs regardless of the assumption of a causal relationship with the study drug(s). The definition, reporting period, and reporting requirements for AEs are described respectively in sections 8.5.1, 8.5.5 and 8.5.8).

Information on AEs must be evaluated by a physician.

Each AE is to be classified by the investigator as serious or non-serious (see definition of a SAE in section 8.5.3). This classification will determine the reporting procedure for the event.

In addition, the frequency, seriousness (see section 8.5.3), severity (see section 8.5.6), and causality (see section 8.5.7) assessment of AEs will be described.

Non-serious AEs are to be reported in the CRF, including description of the event, onset date, duration, severity, seriousness, relationship to all study drugs, actions taken and outcome.

In the CRF, a given AE will be recorded only once per subject, and the severity recorded will be the maximum level reached. If several distinct episodes of the same condition occur, their number will be recorded in the CRF.

SAEs will be reported both on the AE page of the CRF and the SAE forms.

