# 8.5.5. Adverse event reporting period

The AE reporting period begins upon subject enrolment in the trial (after signature of the informed consent) and ends at the EoS visit (Month 4).

All AEs that occur during the AE reporting period specified in the protocol must be reported to DNDi, whether or not the event is considered medication related. In addition, any AE that occurs subsequent to the AE reporting period that the investigator assesses as possibly related to the investigational medication should also be reported as an AE.

For the screen failure subjects, only serious study-related events will be followed-up beyond the date of screening failure (to be recorded).

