## 8.5.6. Grading of adverse event severity

For each serious and non-serious AEs, the investigator is required to assess the severity of each AE.

The severity is a clinical determination of the intensity of a specific event.

The severity of the AE will be graded according to the National Cancer Institute's Common Terminology Criteria for Adverse Events (NCI CTCAE, version 4.03) as a guide in the grading of the severity of AEs.

In case of an AE is not described in the CTCAE version 4.03, the investigator will use the terminology MILD, MODERATE, or SEVERE to describe the maximum severity of the AE. This information will be entered in the AE page of the CRF. For purposes of consistency, these severity grades are defined as follows:

- MILD: The subject is aware of the event or symptom, but the event or symptom is easily tolerated (e.g. no reduction in daily activities is required).
- MODERATE: The subject experiences sufficient discomfort to interfere with or reduces his or her usual level of activity.
- SEVERE: Significant impairment of functioning: the subject is unable to carry out usual activities and/or the subject's life is at risk from the event.
- LIFE-THREATENING: The subject is at significant risk of life; it does not refer to an event which hypothetically might have caused death if it were more severe (life-threatening consequences, urgent intervention required).
- DEATH: Death related to an event.

When the intensity of an AE changes over time, each change in intensity will be recorded in the source documents until the event resolves. However, only one AE and the maximum intensity will be recorded in the CRF for each separate event. If the AE resolves but then recurs, each will be recorded as a separate AE, with the appropriate start and stop times.

There is a distinction between severity and seriousness: a severe AE is not necessarily a serious event.

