The AE can occur in both periods for the same subject (i.e. the event is still present at the second time period). However, for the period analysis the AE start date will be used to identify AEs in each period. The denominator of occurrence rate in each period will respectively be the number of subjects who receive at least one tablet of study treatment during the first time period and the number of subjects attending the 4-month visit or have reported a TEAE during the second time period. All statistics will be provided per time period to separately assess and interpret early events probably attributed to study treatment and late events that could be attributed to the disease or are persistent.

The time course of treatment effect will be analysed using the log rank test stratified by study centre and will be performed on the time to occurrence of TEAEs, taking into account the attrition rate of subjects who are being followed up. A loss to follow-up or a withdrawal will be censored at the time of the last attended visit. The Kaplan-Meier estimates of the proportion of subjects without any TEAE in each treatment group will be presented graphically to assess the time course of the response.

The hierarchy of testing reflects the sequence of testing from the more general effect to the most specific effect. There is a multiplicity of testing issue and an inflation of type I error that cannot be discarded. However, no adjustments of type I error are planned for this study as this study has been designed to detect any potential safety issues rather than confirming and investigating a safety concern.

The rate of occurrence of AEs will be analysed by the true positive status (subjects with parasites detected during the follow up period) in either treatment or placebo groups.

The rate of conversion to parasite positive and the rate of return to seronegative over 4 months will be analysed descriptively using frequency and proportion by treatment group.

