3.2. Treatment Emergent AE definition

The information on adverse events will be collected from the time of signing ICF. The treatmentemergent adverse events (TEAEs) will be defined as events occurring from administration of study drug or events starting before study drug administration but worsening after study drug administration to 4 months post-treatment.

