5.1. Primary Objective Analysis

The assessment of the safety of a single dose of acoziborole compared to placebo during a follow up period of 4 months will be conducted using excess rate (ER) of occurrence of any TEAE over the first 4 months in the acoziborole group compared to placebo. The numerator of the occurrence rate will be the number of subjects with at least one TEAE and the denominator will be the number of subjects in the Safety Set. In addition, a sensitivity analysis will be performed on safety set population excluding subjects with treatment misallocation. The ER is the occurrence rate of any TEAE in the acoziborole group minus the occurrence rate in the placebo group. The 95% confidence interval (CI) of the excess rate will be calculated using Wilson score interval (which provides average coverage very close to 95% in all cases⁹). The excess rate (ER) of occurrence of any TEAE will be transformed to the number of subjects needed to treat (NNT) to observe one more subject with a TEAE in the acoziborole group compared to placebo (NNT = 1 / ER).

The analysis will be performed on the total SS population and by age groups (defined as adolescents aged 15-17 years and adults aged \geq 18 years), gender, TEAE severity category and period of occurrence. Four categorizations of TEAEs per severity will be derived as 1) Serious AEs regardless of the relationship to drug, 2) severe and related to drug TEAEs and 3) mild and/or moderate regardless of relationship to drug, and 4) severe but not related to drug. TEAEs period of occurrence will be categorized as: 1) Occurrence during the hospitalization period and 2) Occurrence after the hospitalization period (from EoH to month 4). The same event for the same subject can occur at both periods (i.e., the event is still present at the second period). However, for the analysis the AE start date will be used to identify AEs in each period. The denominator of occurrence rates will be the number of subjects receiving at least one tablet of IP for the first period and the number of subjects attending the 4-month visit or having reported a TEAE during the second period.

The occurrence rate analysis will be performed on a safety set. MedDRA preferred terms of TEAE with occurrence rates ≥1% in one treatment group will be compared between treatment groups on the excess rates and NNT for any TEAE, by TEAE severity to assess whether the more severe

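### Protocol 8.5.4 and 8.5.6 give conflicting rules for recording recurrent adverse events, and under 8.5.4 recurrences after discharge can be missed in the period analysis and event counts

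*Protocol*

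**What the plan says.** Two protocol sections tell the site how to enter a recurrent event in the CRF.

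- Protocol 8.5.4: "a given AE will be recorded only once per subject, and the severity recorded will be the maximum level reached". The next sentence adds: "If several distinct episodes of the same condition occur, their number will be recorded in the CRF". The same section lists what a non-serious record contains: "Non-serious AEs are to be reported in the CRF, including description of the event, onset date, duration" and further items, with a single onset date.
- Protocol 8.5.6: one entry at maximum intensity for each separate event, and "If the AE resolves but then recurs, each will be recorded as a separate AE, with the appropriate start and stop times".

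The analysis depends on those dates. AE collection starts at consent, before dosing (Protocol 8.5.5). SAP 3.2 counts as treatment-emergent any event occurring from study drug administration, and also "events starting before study drug administration but worsening after study drug administration to 4 months post-treatment". For the split into hospital and post-discharge periods, Protocol 10.7.1 says "for the period analysis the AE start date will be used to identify AEs in each period", and SAP 5.1 says the same: "for the analysis the AE start date will be used to identify AEs in each period". SAP 5.2.2 tabulates numbers of events as well as numbers of subjects.

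**The concern.** If a site follows 8.5.4, an event that occurs in hospital, resolves and returns at home is one record with one start date. If that date is the hospital one, the later episode does not exist for the post-discharge analysis. An event that began between consent and dosing and came back after dosing is one record that may carry a pre-dose date.

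The period split has a stated purpose. Protocol 10.7.1 uses it to separate early events, probably due to treatment, from late or persistent ones. SAP 5.1 repeats the excess rates by period so that late events are not hidden among all events. If sites differ in the rule they follow, post-discharge rates and event counts will partly reflect recording practice.

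**Working it through.** The plan states no figure on this point, so there is none to reproduce. The check compares the texts and then classifies three example subjects.

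**Can the two rules be reconciled?** One could read the AE in 8.5.4 as a single episode, which would match 8.5.6. The following sentence of 8.5.4 rules this out: it deals expressly with distinct episodes and keeps only how many there were. Both sections govern CRF entry, so the conflict stands.

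**Does anything later restore the lost dates?** SAP 3.3 imputes missing or partial dates only. A collapsed record has a complete, valid start date, so no imputation is triggered. Protocol 8.5.3 asks for the date on which an AE becomes serious, which helps for SAEs only.

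**Example classification.** Dosing is on D1 and discharge on D5. An episode is a TEAE if it starts on or after D1. It is in the hospital period if it starts from D1 to D5, and post-discharge if it starts after D5. Section 8.5.4 does not say which onset date is kept, so both choices are shown. The recurrence is assumed not to be judged worse.

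| Episode starts | 8.5.6 | 8.5.4, first onset kept | 8.5.4, last onset kept |
|---|---|---|---|
| D-1 and D3 | 1 TEAE, hospital | 0 TEAEs | 1 TEAE, hospital |
| D2 and D60 | 2 TEAEs, one per period | 1 TEAE, hospital only | 1 TEAE, post-discharge only |
| D-1 and D60 | 1 TEAE, post-discharge | 0 TEAEs | 1 TEAE, post-discharge |

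In the second row one episode loses its date whichever onset is kept. In the first and third rows the result depends on a choice that the protocol leaves open. The worsening route in SAP 3.2 cannot be checked from the collapsed record, because that record holds one maximum severity with no date for it.

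**Which outputs change?**

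- Event counts (SAP 5.2.2): directly, since two episodes become one record.
- By-period preferred-term comparisons (SAP 5.1): directly, since the recurrence is by nature the same condition.
- Any TEAE in the post-discharge period: only for subjects with no other TEAE starting after discharge. The denominator is those who attend the 4-month visit or report a second-period TEAE. A subject who misses that visit and whose only late event was collapsed therefore leaves both numerator and denominator.
- Any TEAE over 4 months: it is yes or no per subject. A recurrence of something already counted as a TEAE changes nothing. Status changes only if the sole post-dose event is a recurrence, not judged worse, of an AE that began between consent and dosing. The schedule puts that window at D-2 to D1H0.
- Time to first TEAE: only if the first post-dose event is such a recurrence.

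**The case against.** The strongest reply accepts the conflict in wording and disputes the consequence. Much of it stands.

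- **The primary endpoint is nearly untouched.** Correct. The pre-dose window is short, and Protocol 8.5.1 does not treat conditions present at the initial visit that do not worsen as AEs. A reader might infer that the main excess rate is at risk. The documents support that only in the narrow case set out above.
- **Loss of TEAE status is not automatic.** Also correct. Protocol 8.5.1 counts worsening in frequency as well as severity for pre-existing conditions, and SAP 3.2 could be read to cover any post-dose occurrence. The undated record remains a problem under either reading.
- **Unequal loss by arm is not shown.** A reader might reason that 97.7% of related TEAEs in the pivotal study fell within 5 days (Protocol 3.3), so more acoziborole subjects would have late recurrences absorbed into a hospital-dated record. The documents do not establish this. The pivotal study was open-label (Protocol 1.6) and no placebo rate from it is given. Protocol 1.4 reports similar AE frequency and severity on active and placebo in healthy volunteers. The 97.7% also leaves only 100 - 97.7 = 2.3% of related TEAEs after day 5, which does not suggest frequent late recurrence, although how that study recorded repeat episodes is not stated.
- **Sites may have followed 8.5.6.** Possible. Protocol 8.5.8 refers to an eCRF completion guideline that is not among the documents and may settle actual practice. It would not remove the contradiction from the protocol.

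**Conclusion.** The contradiction is real and should be corrected. The once-per-subject rule cannot supply what the analysis needs: a start date and a severity for each episode. The exposed outputs are the post-discharge period analysis, the by-period preferred-term comparisons and the event counts. The any-TEAE primary endpoint and time to first TEAE are exposed only through recurrences, not judged worse, of AEs that began between consent and dosing.

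No size can be given. The documents contain no recurrence rates, do not say which onset date a collapsed record keeps, and do not show which rule sites used. For the same reasons no direction or difference by arm can be claimed. The conclusion rests on the wording of the sections cited and on the use of AE start date in Protocol 10.7.1 and SAP 5.1.

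**What to change.** 1. In Protocol 8.5.4, delete both sentences of the paragraph (the once-per-subject rule and the episode count) and let 8.5.6 govern: each episode that resolves and recurs is its own entry with start date, stop date and severity.
2. Align the eCRF completion guideline.
3. Protocol 9.2 already describes 1.5 years of conduct, so a change of text will not restore dates in records already collapsed. Before database lock, query source documents for the start date, stop date and severity of each episode in any record with more than one episode. Protocol 8.5.4 requires all AEs in source documents, and 8.5.6 requires changes in intensity there, so the information should be retrievable.
4. State in the SAP (3.2 and 5.1) that the TEAE and period flags are derived per episode.

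The cost is a protocol clarification, a guideline update, a short SAP addition, a few more AE entries and a limited set of data queries.

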# 8.5.5. Adverse event reporting period

The AE reporting period begins upon subject enrolment in the trial (after signature of the informed consent) and ends at the EoS visit (Month 4).

All AEs that occur during the AE reporting period specified in the protocol must be reported to DNDi, whether or not the event is considered medication related. In addition, any AE that occurs subsequent to the AE reporting period that the investigator assesses as possibly related to the investigational medication should also be reported as an AE.

For the screen failure subjects, only serious study-related events will be followed-up beyond the date of screening failure (to be recorded).

## 8.5.6. Grading of adverse event severity

For each serious and non-serious AEs, the investigator is required to assess the severity of each AE.

The severity is a clinical determination of the intensity of a specific event.

The severity of the AE will be graded according to the National Cancer Institute's Common Terminology Criteria for Adverse Events (NCI CTCAE, version 4.03) as a guide in the grading of the severity of AEs.

In case of an AE is not described in the CTCAE version 4.03, the investigator will use the terminology MILD, MODERATE, or SEVERE to describe the maximum severity of the AE. This information will be entered in the AE page of the CRF. For purposes of consistency, these severity grades are defined as follows:

- MILD: The subject is aware of the event or symptom, but the event or symptom is easily tolerated (e.g. no reduction in daily activities is required).
- MODERATE: The subject experiences sufficient discomfort to interfere with or reduces his or her usual level of activity.
- SEVERE: Significant impairment of functioning: the subject is unable to carry out usual activities and/or the subject's life is at risk from the event.
- LIFE-THREATENING: The subject is at significant risk of life; it does not refer to an event which hypothetically might have caused death if it were more severe (life-threatening consequences, urgent intervention required).
- DEATH: Death related to an event.

When the intensity of an AE changes over time, each change in intensity will be recorded in the source documents until the event resolves. However, only one AE and the maximum intensity will be recorded in the CRF for each separate event. If the AE resolves but then recurs, each will be recorded as a separate AE, with the appropriate start and stop times.

There is a distinction between severity and seriousness: a severe AE is not necessarily a serious event.

